Cortical area	0 – 24 months				
femoral neck					

Cortical area inter- trochanteric regions	0 – 24 months					
Cortical area sub-	0 – 24 months					
trochancheric						
regions						
Bone microstructure (cm)					
Cortical thickness	0 – 24 months					
sub-trochancheric						
regions						
Cortical thickness	0 – 24 months					
femoral neck						
Cortical thickness	0 – 24 months					
inter-trochanteric						
regions						
Cortical thickness	0 – 24 months					
sub-trochancheric						
regions						
Estimated bone strength						
CSMi (cm4)	0 – 24 months					
Section Modulus	0 – 24 months					
(cm3)						

Supplementary Table S1. Sensitivity analysis: Primary outcome with imputation

If more than 5% of observations are missing at 24 months for the main analysis of the primary outcomes reported in Table 2 the analysis will be repeated using multiple imputation (assuming missing at random) by linear regression with all baseline characteristics included in Table 1 as covariates generating 100 imputation sets. Results will be reported in a table structured as Table 2.

Supplementary Table S2. Main analyses adjusted for baseline characteristics

Main analysis as included in Table 2 will be repeated adjusted for D vitamin level and calcium intake at baseline as numerical covariates. The adjusted results will reported in a table structured as Table 2.

Supplementary Table S3. Mean and standard deviation of outcomes at baseline and 24 months

Mean and standard deviation (SD) for all outcomes stratified by treatment group will be reported at baseline and at 24 months.

	Baseline		24 months		
	Vitamin K +D Placebo group		Vitamin K +D	Placebo group	
	group		group		
	Mean (SD)	Mean (SD)	Mean (SD)	Mean (SD)	
Primary outcomes					
Volumetric BMD in					
spine					

Volumetric BMD in			
hip			
Secondary outcome	S		
Volumetric bone mi	neral density (mg/cm3	3)	
Trabeculært vBMD			
total hip			
Trabeculært vBMD			
femoral neck			
Trabeculært vBMD			
inter-trochanteric			
regions			
Trabeculært vBMD			
sub-trochancheric			
regions			
Cortical vBMD			
total hip			
Cortical vBMD			
femoral neck			
Cortical vBMD			
inter-trochanteric			
regions			
Cortical vBMD			
sub-trochancheric			
regions			
Bone geometry (cm2	2)		
Trabecular area			
sub-trochancheric			
regions			
Trabecular area			
femoral neck			
Trabecular area			
inter-trochanteric			
regions			
Trabecular area			
sub-trochancheric			
regions			
Cortical area sub-			
trochancheric			
regions			
Cortical area			

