All analyses were performed in the intention-to-treat population and as superiority analyses. Two-sided p-values of 0.05 or less were considered to indicate statistical significance and associations and effect estimates will be reported with 95% probability symmetric confidence interval (2.5% to 97.5% quantile).

Practical considerations

Data were collected using REDCap (2, 3) hosted by OPEN (Open Patient data Explorative Network, Odense University Hospital, Odense Denmark) with project number OP_530. Data were analyzed using Stata (4) on OPEN's secure analysis server (OPEN Analyse). A prespecified random seed of 7042021 will be used for bootstrapping and imputation.

Planned analyses for primary publication: Change in AVC score

Exclusion criteria

Participants with AVC < 300 at baseline will be excluded from all analyses in this publication.

Outcomes

Primary outcome: Main analysis

The primary outcome was the change in aortic valve calcification (AVC) score (numerical) from baseline to 24 month for the full cohort of included patients.

Secondary outcomes to be included in the primary publication

Secondary outcomes were

- Change in AVC from baseline to 24 months in two prespecified subgroups (baseline AVC score 300-599 and ≥600).
- Change in AVC from baseline to 12 months and from 12 months to 24 months, both for the full cohort as well as for the two subgroups.
- Changes in aortic valve area from baseline to 24 months (numerical)
- Change in peak aortic-jet velocity from baseline to 24 months (numerical)
- Need of heart valve surgery (dichotomous, occurred / not occurred between baseline and 24 months)

- Change in MGP with different phosphorylation and carboxylation forms (numerical)
- Change in QoL from baseline to 24 months (numerical)

Safety outcomes

Safety outcomes were

- Death (all cause and cardivascular cause) (dichotomous)
- Cardiovascular events (a composite endpoint of myocardial infarction, coronary revascularization, stroke, aortic disease, significant peripheral artery disease (surgery), as well as these endpoints separately) (all dichotomous)
- Progressive aortic valve disease (more than 50% increase in AVC score) (dichotomous)
- Venous thromboembolism (dichotomous)
- Severe bleeding
- Low energy or spontaneous fracture
- Cancer (recurrent cancer or new cancer) (dichotomous)

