- The following laboratory measurements: hemoglobin, leucocytes, thrombocytes, albumin, creatinine (eGFR), urea, calcium, phosphate, magnesium, troponine, creatine kinase, alanine aminotransferase, lactate dehydrogenase, bilirubin, alkaline phosphatase, total-cholesterol, low-density lipoprotein, high-density lipoprotein, parathyroid hormone, vitamin D, prothrombin time-international normalised ratio (PT-INR) and activated partial thromboplastin time (all numerical)

Dichotomous safety outcomes were evaluated as occurred / not occurred between baseline and 24 months. Numerical safety outcomes were evaluated as change from baseline to 12 and 24 months.

Planned tables and figures and corresponding analyses

Table 1. Characteristics of patients at baseline

Characteristics (as listed in Table 1 below, numerical characteristics marked with [numerical]) of patients at baseline will be reported separately for the two treatment groups. Characteristics will be reported as

- Mean and standard deviation (SD) for numerical characteristics, which are approximately
 normally distributed in both treatment groups as investigated by normal quantile-quantile
 plots. These characteristics will be compared between groups by two-sample t-test with
 assumed equal variance, or with assumed unequal variance if indicated by Levene's test for
 equality of variance (5).
- Median and 1st and 3rd quartile (inter quartile range (IQR)) for numerical characteristics, which
 are not approximately normally distributed in at least one treatment group as indicated by
 normal quantile-quantile plots. These characteristics will be compared between groups by
 Wilcoxon rank-sum test.

• Counts and proportions for categorical characteristics (with categories as specified in Table 1 below). These characteristics will be compared between groups by χ^2 -test if all counts are at least 5, or with Fisher's exact test otherwise.

No adjustments for multiple testing will be carried out in Table 1 and no effect sizes for differences between groups will be estimated. Missing observations will be excluded from tests in Table 1, and number of missing observations in each group will be specified.

Characteristic	Vitamin K +D group (N=XX)	Placebo group (N=XX)	P-value
Age – years [numerical]	, ,	, ,	
Baseline AVC – AU [numerical]			
Echocardiography			
Bicuspid aortic valve – no (%)			
V _{max} - cm/sec [numerical]			
Aortic valve area - cm² [numerical]			

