AVC score	0 – 24 months				
(baseline AVC score	0 – 12 months				
300-599)	12 – 24				
	months				
AVC score	0 – 24 months				
(baseline AVC score	0 – 12 months				
≥600)	12 – 24				
	months				
Aortic valve area	0 – 24 months				
Peak aortic-jet	0 – 24 months				
velocity					
dp-ucMGP	0 – 24 months				
QoL	0 – 24 months				

Table 3. Dichotomous secondary outcomes and adverse events

Dichotomous secondary outcomes (valvular surgery between baseline and 24 months) and adverse events are reported as counts and proportions separately for each treatment group and compared between groups by χ^2 -test if all counts are at least 5, or with Fisher's exact test otherwise. If a patient reported multiple events of the same outcomes, this will be handled dichotomously as experiencing the outcome in the analyses, but the count of such patients will be reported in a parenthesis or footnote to the table.

Missing observations will be excluded from tests in Table 2, and number of missing observations in each group will be specified.

Event	Vitamin K +D group	Placebo group	p-value
-------	--------------------	---------------	---------

	(N=XX)	(N=XX)	
Outcome			
Valvular Surgery – no (%)			
Adverse Events			
Any event – no (%)			
Death – no (%)			
Cardiovascular events (combined) – no (%)			
Myocardial infarction			
Coronary revascularization			
Stroke			
Aortic disease			
Peripheral artery surgery			
Progressive aortic valve disease (more than 50%			
increase in AVC score)			
Severe bleeding – no (%)			
Venous thromboembolism – no (%)			
Low energy fracture– no (%)			
Incident cancer – no (%)			

Table 4. Numerical safety outcomes

Numerical safety outcomes will be analyzed by linear mixed models corresponding to the analyses specified for the primary outcome in Table 2. No subgroup analyses will be performed.

		Vitamin K +D group	Placebo group		
		Mean change (95 %	Mean change	Treatment	P-
		CI)	(95 % CI)	effect (95 % CI)	value
hemoglobin	0 - 24 months				
creatinine (eGFR)	0 - 24 months				
calcium	0 - 24 months				
phosphate	0 - 24 months				
parathyroid hormone	0 - 24 months				
vitamin D	0 - 24 months				
activated partial	0 - 24 months				
thromboplastin time					
prothrombin time-	0 - 24 months				
international					
normalised ratio (PT-					
INR)					

Table 5. Stratified analyses of the primary outcome

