Analyses of the primary outcome (AVC score) will be repeated stratifying for age (<70 or ≥70 years at baseline), diabetes (yes / no at baseline), hypertension (yes / no at baseline), atrial fibrillation (yes / no at baseline), ischemic heart disease (yes / no at baseline), renal failure (yes / no at baseline), statin therapy (yes / no at baseline), and MGP (below / above median). In these analyses, patients will not be stratified by baseline AVC score 300-599 and ≥600. The same models as for Table 2 will be applied for these analyses.

	Vitamin K +D group	Placebo group		
	Mean change from baseline (95 % CI)	Mean change from baseline (95 % CI)	Treatment effect (95 % CI)	P-value
Age < 70 years				
Age ≥70 years				
No diabetes				
Diabetes				
No				
hypertension				
Hypertension				
No atrial				
fibrillation				
Atrial				
fibrillation				
No ischemic				
heart disease				
Ischemic heart				
disease				
No renal failure				
Renal failure				
No statin				
therapy				
Statin therapy				
Baseline MGP <				
median				
Baseline MGP				
>= median				

Supplementary Table S1. Sensitivity analysis: Primary outcome and numerical secondary outcomes with imputation

If more than 5% of observations are missing at 24 months for the main analysis of the primary outcome reported in Table 2 the analysis will be repeated using multiple imputation (assuming missing at random) by linear regression with all baseline characteristics included in Table 1 as covariates generating 100 imputation. Results will be reported in a table structured as Table 2.

Supplementary Table S2. Sensitivity analysis: Primary outcome on subgroup with high compliance

The analysis of primary outcome (all patients 0-24 months) will be repeated (with the same methodology as specified for Table 3) on those patients, who reported a compliance of at least 90% during the study period. Furthermore, number and proportion of patients included in this analysis will be reported in Table S4, together with odds ratio (with 95% confidence interval) and p-value determined by univariate logistic regression for difference in compliance rate between treatment arms will be reported.

		Vitamin K +D group	Placebo group	Group difference	
		Number (proportion)	Number (proportion)	Odds ratio (95 % CI)	P-value
Compliance of a	ıl at least 90%	(ριοροιτίση)	(proportion)	Cij	
		Mean change from baseline (95 % CI)	Mean change from baseline (95 % CI)	Treatment effect (95 % CI)	P-value

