score	and						
 Ascending 	12 – 24 months						
 Arcus 							
 Descending 							
 Suprarenal 							
 Infrarenal 							
Renal artery							
Iliaca com artery							
Iliaca ext artery							
Aortic diameter	0 – 12 months						
 Ascending 	and						
Arcus	12 – 24 months						
 Descending 							
Infrarenal							

Table 3. Dichotomous secondary outcomes

Dichotomous secondary outcome (aortic surgery between baseline and 24 months) is reported as counts and proportions separately for each treatment group and compared between groups by χ^2 -test if all counts are at least 5, or with Fisher's exact test otherwise. If a patient reported multiple events of the same outcomes, this will be handled dichotomously as experiencing the outcome in the analyses, but the count of such patients will be reported in a parenthesis or footnote to the table.

Missing observations will be excluded from tests in Table 3, and number of missing observations in each group will be specified.

Event	Vitamin K +D group (N=XX)	Placebo group (N=XX)	p-value
Outcome			
Aortic surgery – no (%)			

Table 4. Stratified analyses of the primary outcome

Analyses of the primary outcome (change in aortic calcification score and change in aortic dilatation) will be repeated stratifying for and MGP (below / above median). The same models as for Table 2 will be applied for these analyses.

Supplementary Table S1. Sensitivity analysis: Primary outcome with imputation

If more than 5% of observations are missing at 24 months for the main analysis of the primary outcome reported in Table 2 the analysis will be repeated using multiple imputation (assuming missing at random) by linear regression with all baseline characteristics included in Table 1 as covariates generating 100 imputation sets. Results will be reported in a table structured as Table 2.

Supplementary Table S2. Sensitivity analysis: Primary outcome on subgroup with high compliance

The analysis of primary outcome will be repeated (with the same methodology as specified for Table 2) on those patients, who reported a compliance of at least 90% during the study period. Furthermore, number and proportion of patients included in this analysis will be reported in Table S5, together with odds ratio (with 95% confidence interval) and p-value determined by univariate logistic regression for difference in compliance rate between treatment arms will be reported.

		Vitamin K +D	Placebo group	Group difference	
		group			
					T

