Change in frequency of level of coronary obstruction (no/nonobstructive/obstructive) from baseline to 24 months will be compared between treatment groups by mixed-effects ordered logistic regression including a random intercept for each patient and a fixed effects interaction between treatment and time point. As baseline measurements are obtained before randomization, treatment at baseline will be modelled as a separate common treatment category, constraining baseline measurements to no systematic treatment effect between the two treatment arms, as suggested in literature (6).

Baseline	24 months follow-up	Group difference

	Vitamin K+D group	Placebo group	Vitamin K+D group	Placebo group	Treatment effect OR	p-value
					(95% CI)	
Coronary obstruct	tion					
Normal – no (%)						
Nonobstructive						
– no (%)						
Obstructive – no						
(%)						
Total						
1 vessel						
2 vessel						
3 vessel						

Table 5. Analysis on cardiovascular events

Events from baseline to 24 months follow-up will be reported as counts and proportions and will be compared between groups by logistic regression estimating OR with 95% CI.

	Vitamin K+D group	group Placebo group Group diffe		erence	
	Number (%)	Number (%)	OR (95% CI)	p-value	
Events					
Myocardial infarction					
PCI procedure					
CABG surgery					
All cause death		_			

Supplementary table S1. Adjusted analyses of the primary outcome

Results from an adjusted analysis of the primary outcome, mean change in CAC score from baseline to 24 months follow-up. The analysis will be performed as a regression adjusting for known cardiovascular risk factors (those included in Table S1) to further investigate the treatment effect.

	Coefficient change baseline to 24 months (95% CI)	p-value
Intervention (Vitamin K+D)		
Predictor variable		
Age, yrs		
BMI, kg/m ²		
Diabetes		
Hyperlipidemia		
Hypertension		
Atrial fibrillation		
Renal failure		
Family history of premature CVD		
Smoking status		

Former smoker	
Active smoker	
CAC score ≥ 400 AU	

Supplementary table S2. Analysis on compliant patients

Analysis on patients with compliance > 90% from baseline to 24 months.

		Vitamin K +D group	Placebo group	Group difference	2		
		Number (proportion)	Number (proportion)	Odds ratio (95 % CI)	P-value		
Compliance of at	t least 90%	(proportion)	(ргорогион)	NA NA			
		Mean change from baseline (95 % CI)	Mean change from baseline (95 % CI)	Treatment effect (95 % CI)	P-value		

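### Excluding missing patients from the 24-month event tests keeps withdrawals who already had an event and drops event-free ones, if event follow-up ends at withdrawal

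*SAP*

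**What the plan says.** All of this is in the SAP.

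- **Primary publication, secondary outcomes.** Valve surgery is a fixed-window binary outcome: "Need of heart valve surgery (dichotomous, occurred / not occurred between baseline and 24 months".
- **Primary publication, safety outcomes.** "Dichotomous safety outcomes were evaluated as occurred / not occurred between baseline and 24 months".
- **Primary publication, Table 3.** Counts and proportions by arm are compared by a chi-square "test if all counts are at least 5, or with Fisher's exact test otherwise. If a patient reported multiple events". The missing-data rule is "Missing observations will be excluded from tests in Table 2, and number of missing observations in each group will be specified".
- **Aortic publication, Table 3 (aortic surgery).** The same rule with the expected table number: "Missing observations will be excluded from tests in Table 3, and number of missing observations in each group will be specified".
- **Coronary publication, Table 5.** "Events from baseline to 24 months follow-up will be reported as counts and proportions and will be compared between groups by logistic regression". Nothing is said there about incomplete follow-up.

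The SAP does not define a missing observation for an event outcome. It does not say whether events are still collected after withdrawal. No time-to-event analysis is planned. The imputation analysis (primary publication, Table S1) is by linear regression, is triggered "If more than 5% of observations are missing at 24 months for the main analysis of the primary outcome reported in Table 2", and is laid out like Table 2, so it does not reach the event outcomes.

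**The concern.** With a yes/no outcome over a fixed window, an event settles a patient's status as soon as it happens. Being event-free is settled only at 24 months. Take two patients who withdraw at month 12 and are not followed further. One had a stroke at month 6: the outcome is known and the patient counts in numerator and denominator. The other had no event: status at 24 months is unknown, so the patient is missing and excluded. Whether a withdrawn patient is kept therefore depends on the outcome itself, and the excluded patient's 12 event-free months are lost.

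Two things are at stake. The reported event proportions are too high, increasingly so as withdrawal rises. And if one arm loses more patients, that arm looks more harmful without any true difference. This matters most for the safety table, where readers take the proportions at face value. It also fits poorly with the SAP's statement that all analyses are by intention to treat.

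**Working it through.** **Cross-reference.** In the primary publication the exclusion sentence stands in the Table 3 section but names Table 2. Table 2 holds numerical outcomes analysed by mixed models and has its own sentence on missing data. The matching sentence in the aortic publication names Table 3. The number is a slip; read literally, the primary Table 3 has no missing-data rule.

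**Inputs.** The SAP gives no event or withdrawal rates for these outcomes, so there is no planned figure to reproduce. The following are assumptions: true 24-month risk p, the same in both arms; constant hazard; a fraction w of patients withdrawing evenly over 24 months; withdrawal unrelated to risk; no event follow-up after withdrawal. From the SAP: 400 patients planned, 1:1, so 200 per arm.

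**Formulas.** With H = −ln(1 − p), the chance that a withdrawing patient had an event before leaving is q = 1 − p/H.
- Event-free withdrawals excluded: [(1 − w)p + wq] / [(1 − w) + wq].
- Withdrawals without an event counted as not occurred: (1 − w)p + wq.

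**Numbers for p = 15%.** H = 0.1625 and q = 1 − 0.15/0.1625 = 0.0770.
- w = 5%: numerator 0.95 × 0.15 + 0.05 × 0.0770 = 0.1464; denominator 0.95 + 0.0039 = 0.9539; result 15.34%.
- w = 20%: numerator 0.80 × 0.15 + 0.20 × 0.0770 = 0.1354; denominator 0.80 + 0.0154 = 0.8154; result 16.61%.

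In patients, for the arm with 20% withdrawn: 160 complete follow-up with 24 events, and 40 withdraw, of whom 3.08 had an event first. The rule gives 27.08/163.08 = 16.6%.

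| True risk, both arms | Excluded: 5% vs 20% withdrawn | Difference | Counted as not occurred |
|---|---|---|---|
| 5% | 5.1% vs 5.6% | +0.5 points | – |
| 15% | 15.34% vs 16.61% | +1.3 points | 14.64% vs 13.54% (−1.1 points) |
| 20% | 20.43% vs 22.02% | +1.6 points | 19.52% vs 18.07% (−1.5 points) |

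The last column shows what follows if the analyst scores withdrawals as event-free instead: the sign reverses.

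**Effect on the test.** A second calculation used a constant withdrawal hazard, true risks of 5% to 20%, 200 per arm before exclusions and a nominal two-sided 5% level.
- Equal withdrawal (10% in each arm), no treatment effect: difference 0, type I error 5.0%.
- 5% vs 15% withdrawn: false difference of 0.3 to 1.0 points, type I error 5.2% to 5.6%.
- 10% vs 30% withdrawn: false difference of 0.7 to 2.3 points, type I error 5.8% to 8.0%.

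**Scale against noise.** At 15% risk with 200 per arm, the standard error of a difference is √(2 × 0.15 × 0.85/200) = 3.6 points, so a bias of 1.3 points is about 0.36 standard errors.

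**The case against.** The strongest reply is that the SAP prescribes no such asymmetry. It leaves the missing observation undefined, and whether events are followed after withdrawal may be settled in the protocol, which is not at hand. If every patient's events are known to 24 months, nobody is missing and the bias disappears. That stands, and the conclusion is conditional on it.

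It is also fair that the distortion is small beside sampling error unless withdrawal differs sharply by arm, that the SAP requires missing counts by group so an imbalance would be visible, and that chi-square or Fisher tests on proportions are conventional for secondary and safety outcomes over one fixed window. These points limit the size. They do not justify a rule that discards event-free follow-up when a standard method uses it.

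Two stronger readings are tempting and are not supported.

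- A reader might infer that the plan counts death before valve surgery as no need of surgery. The SAP does not say so. Death is a separate safety outcome, "Death (all cause and cardivascular cause) (dichotomous", and nothing links it to the scoring of surgery; such a patient could equally be treated as missing. Cumulative incidence with death as a competing event also counts that patient as never having had surgery, so this scoring would not in itself be an error.
- A reader might infer a fault in the different denominators for the same events in the primary and coronary publications. They differ by design: the coronary publication excludes patients with previous myocardial infarction, PCI or CABG, and the primary publication excludes only those with baseline AVC below 300.

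**Conclusion.** The point holds conditionally. If event follow-up ends at withdrawal, the exclusion rule makes inclusion depend on the outcome, biases event proportions upward, and distorts the arm comparison when withdrawal differs by arm. Under assumed rates (15% true risk in both arms, 5% versus 20% withdrawn, constant hazard, uniform withdrawal unrelated to risk) a true difference of zero appears as 15.3% versus 16.6%. With equal withdrawal and no treatment effect the difference is zero, although both proportions are still inflated. With complete ascertainment there is no bias. If withdrawal is related to risk, these figures do not apply and the distortion can be larger.

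The primary outcome is not affected. This is an inexpensive improvement to the analysis of secondary and safety outcomes, together with one plain error in a table number.

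**What to change.** 1. In the primary publication's Table 3 section, change the table number in the missing-data sentence from 2 to 3.
2. Analyse valve surgery, aortic surgery and the clinical safety events by time from randomisation to first event, censoring at last contact. Report cumulative incidence to 24 months by arm, with death as a competing event for non-fatal outcomes, and compare arms by a log-rank test or cause-specific hazards.
3. Handle incomplete follow-up in the same way for the events in the coronary publication's Table 5.
4. Keep the scan-based row (AVC increase of more than 50%) as a proportion, because it is known only when a scan is done.
5. State whether events are collected after withdrawal. If ascertainment to 24 months is complete, cumulative incidence equals the simple proportion and nothing is lost by the change.

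The cost is SAP wording and standard Stata survival commands. Event dates and last-contact dates must be in the database, and rows with few events will remain imprecise. Censoring at last contact still assumes that withdrawal is unrelated to later risk.
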